#### 4.3.6 Radiotherapy Timing:

Quad-Shot Radiotherapy in Combination with Immune Checkpoint Inhibition for  
Advanced/Recurrent Head and Neck Cancer  
Wake Forest Baptist Comprehensive Cancer Center  
WFBCCC60320

- Radiation Therapy will be given as outlined in the Study Schema and according to the Study Calendar in Section 6.1:
  - Quad-shot Cycle #1: prior to cycle 4 (between pembrolizumab cycle 2-3 or 3-4) for all patients
  - Quad-shot Cycle #2 (if delivered): prior to cycle 8 (between pembrolizumab cycles 6-7 or 7-8)
  - Quad-shot Cycle #3 (if delivered): prior to cycle 13 (between pembrolizumab cycles 11-12 or 12-13).
- Radiotherapy is **NOT** to be given on the same day as immunotherapy/ICI infusion.
- Outside of this restriction, the timing of the delivery of 4 radiotherapy fractions that make up each cycle is not required.
- Though specific days are not mandated, it is **strongly recommended** that at least 1 day of the two consecutive days (including 2 of the 4 planned RT fractions per cycle) falls within 7 days prior to the delivery of an immunotherapy infusion.

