- c. With first administration of pembrolizumab only and then as clinically indicated. Subjects will have their blood pressure and pulse measured before, during and after the infusion at the following times (based on a 60-minute infusion):
  - At the beginning of the infusion (at 0 minutes)
  - At 30 minutes during the infusion ( $\pm 5$  minutes)
  - At the end of the infusion (at 60 minutes  $\pm 5$  minutes)
  - In the 1 hour observation period post-infusion: 30 and 60 minutes after the infusion (ie, 90 and 120 minutes from the start of the infusion) ( $\pm 5$  minutes) – for the first infusion only and then for subsequent infusions as clinically indicated
  - If the infusion takes longer than 60 minutes then blood pressure and pulse measurements should be collected every 30 minutes ( $\pm 5$  minutes) and as described above or more frequently if clinically indicated.
- d. ECG during screening and at Day1 –baseline. Thereafter as clinically indicated. Baseline and abnormal ECG at any time in triplicate others single. Triplicate EKG is only needed at screening, and not on Cycle 1 Day 1 unless something clinically significant was seen at screening.
- e. Free T3 and free T4 will only be measured if TSH is abnormal. They should also be measured if there is clinical suspicion of an adverse event related to the endocrine system.
- f. CT (preferred) or MRI scans, preferably with IV contrast, are collected during screening (for baseline) and as close to and prior to initiation of study treatment but not more than 14 days  $\pm$  5 days prior to first treatment. Will then be performed every 5 cycles ( $\pm$  1 cycle) for tumor response measurement
- g. PET scan will be performed in all cases if reimbursed by Medical Insurance or funded. It will be performed as close to the initiation of treatment but not more than 28 days prior to treatment. Will then be performed in follow up as clinically indicated and if approved by medical insurance.

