### **6.6 Criteria for Removal from Study**

Patients will be removed from study when any of the following criteria apply:

Quad-Shot Radiotherapy in Combination with Immune Checkpoint Inhibition for Advanced/Recurrent Head and Neck Cancer  
Wake Forest Baptist Comprehensive Cancer Center  
WFBCCC60320

- Patient withdrawal of consent or loss to follow-up.
- Adverse event that, in the opinion of the investigator or the sponsor, contraindicates further dosing.
- Subject is determined to have met one or more of the exclusion criteria for study participation at study entry and continuing investigational therapy might constitute a safety risk.
- Pregnancy or intent to become pregnant
- Grade  $\geq 3$  infusion reaction.
- Subject noncompliance that, in the opinion of the investigator or sponsor, warrants withdrawal; eg, refusal to adhere to scheduled visits.
- Initiation of alternative anticancer therapy including another investigational agent.
- Confirmation of PD and investigator determination that the subject is no longer benefiting from protocol treatment.
- Death.

Subjects who are permanently discontinued from further receipt of investigational product, regardless of the reason (withdrawal of consent, due to an AE, other), will be identified as having permanently discontinued treatment.

Subjects who are removed from study prior to completing at least 2 cycles of ICI followed by at least 1 cycle of quad-shot radiotherapy followed by at least 2 cycles of ICI will be discontinued from the study and replaced.

Subjects who are permanently discontinued from receiving investigational product will be followed for safety until follow-up criteria are met in Section 6.4. Subjects who decline to return to the site for evaluations will be offered follow-up by phone for at least 60 days as an alternative.

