## **7.0 Measurement of Effect**

### **7.1 Antitumor Effect – Solid Tumors**

In accordance with the standard of care, after a baseline scans obtained prior to study registration, patients will be reevaluated for response after 5 cycles of immunotherapy. Patients who continue to receive ICI at the discretion of the medical oncologist will be evaluated again after 10 cycles of ICI.

Response and progression will be evaluated in this study using the Response Evaluation Criteria in Solid Tumors (RECIST) criteria 1.1.(40) Changes in the largest diameter

(unidimensional measurement) of the tumor lesions and the shortest diameter in the case of malignant lymph nodes are used in the RECIST criteria.

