### 7.1.1 Definitions

- **Evaluable for toxicity:**

Only those patients who have received at least 1 fraction of radiotherapy and at least 1 cycle of ICI will be evaluable for toxicity from the time of their first fraction of radiotherapy.

- **Evaluable for objective response:**

Only those patients who received at least one cycle of quad-shot radiotherapy (given after at least 2 cycles of ICI), and have had their target disease re-evaluated will be evaluable. These patients will have their response classified according to the definitions stated below.

Note: Per Section 6.6, subjects who are removed from study prior to completing at least 2 cycles of ICI followed by at least 1 cycle of quad-shot radiotherapy followed by at least 2 cycles of ICI will be discontinued from the study and replaced.

- **Evaluable Non-Target Disease Response.**

Patients who have lesions present at baseline that are evaluable but do not meet the definitions of target disease, have received at least one cycle of quad-shot radiotherapy, and have had their disease re-evaluated will be considered evaluable for non-target disease. The response assessment is based on the presence, absence, or unequivocal progression of the lesions.

- **Measurable disease / measurable lesions**

Measurable lesions are defined as those that can be accurately measured in at least one dimension (longest diameter to be recorded) as  $\geq 20$  mm by chest x-ray, as  $\geq 10$  mm with CT scan, or  $\geq 10$  mm with calipers by clinical exam. All tumor measurements must be recorded in millimeters (or decimal fractions of centimeters).

- **Malignant lymph nodes.**

To be considered pathologically enlarged and measurable, a lymph node must be  $\geq 15$  mm in short axis when assessed by CT scan (CT scan slice thickness recommended to be no greater than 5 mm). At baseline and in follow-up, only the short axis will be measured and followed.

- **Non-measurable disease / non-measurable lesions:**

All other lesions (or sites of disease), including small lesions (longest diameter  $<10$  mm or pathological lymph nodes with  $\geq 10$  to  $<15$  mm short axis), are considered non-measurable disease. Bone lesions, leptomeningeal disease, ascites, pleural/pericardial effusions, lymphangitis cutis/pneumonitis, inflammatory breast disease, and abdominal masses (not followed by CT or MRI), are considered as non-measurable.

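### Early failures are replaced and leave the response-rate denominator, so the ORR is likely to read high, and no rate that keeps them is planned

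*Combined protocol and SAP*

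**What the plan says.** Section 6.6 sets a minimum sequence of at least two ICI cycles, at least one quad-shot cycle, and at least two more ICI cycles. Anyone removed before finishing it is replaced: the sentence ends "radiotherapy followed by at least 2 cycles of ICI will be discontinued from the study and replaced". It makes no exception by reason. The removal reasons listed above it include death, adverse events that rule out further dosing, and "Confirmation of PD and investigator determination that the subject is no longer benefiting from protocol treatment". They also include reasons that say nothing about response, such as "Patient withdrawal of consent or loss to follow-up".

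Section 7.1.1 defines who is evaluable for objective response: patients irradiated after at least two ICI cycles "and have had their target disease re-evaluated will be evaluable". A Note under that definition repeats the replacement rule ("Note: Per Section 6.6, subjects who are removed from study prior to completing at least 2 cycles of ICI" and so on). Section 11.3 sets the sample at 15 patients evaluable under Section 7.1.1. Section 11.1 plans one ORR with one Clopper-Pearson interval.

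On timing, Section 4.3.6 places the first quad-shot "prior to cycle 4 (between pembrolizumab cycle 2-3 or 3-4) for all patients". Section 7.1 says "patients will be reevaluated for response after 5 cycles of immunotherapy". Footnote f of the Section 6.1 calendar says of CT or MRI "Will then be performed every 5 cycles", with a window of plus or minus one cycle.

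**The concern.** A patient who dies, stops for toxicity, or progresses clinically before completing the sequence usually has no response scan and is most likely a non-responder. Under the plan that patient is replaced by someone who got further. The reported ORR is then conditional on surviving and tolerating roughly the first 9 to 15 weeks.

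Section 11.3 gives the ORR a practical use: it anticipates that the rate must be at least as high as the 13% to 36% seen before if further studies are to be warranted. If early failures are left out, the rate can look better against that range than the rate among all who started. The plan provides neither a second rate nor a replacement count from which a reader could see the difference.

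**Working it through.** **Inputs.** From the documents: 15 evaluable patients and a maximum interval width of 0.52 (Section 11.3); three-week cycles (Schema, Section 4.4.2); median survival of 12 months or more (Section 1); and 17% as an illustrative true ORR (a pembrolizumab-alone row of Table 1). Assumptions: exponential survival from registration, treatment starting at registration, 4.348 weeks per month, and an 18-month median as a second case. The documents give no replacement rate.

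**1. The plan's own figure.** The exact 95% interval for 7/15 is 0.213 to 0.734, width 0.5215. This matches the stated 0.52.

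**2. Timing.** Take cycle 1 as week 0. With quad-shot between cycles 2 and 3, the sequence is complete at cycle 4, in week 9. With quad-shot between cycles 3 and 4, it is complete at cycle 5, in week 12. Five full cycles end at week 15, when the first response assessment is due. A death before week 9 or 12 leads to replacement. A death after that but before the scan ordinarily leaves no repeat assessment, so the patient is not evaluable under Section 7.1.1.

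**3. Size of the bias in general.** Let p be the true rate in everyone, f the fraction left out, and r the response rate among those left out. The expected reported rate is (p − f·r)/(1 − f). With p = 0.17 and f = 0.15:
- r = 0: 0.17/0.85 = 20.0%
- r = 0.17: (0.17 − 0.0255)/0.85 = 17.0%, so no bias

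If f = 0 there is no bias either.

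**4. Deaths only, r = 0.** f = 1 − 2^(−t/median), and the reported rate is 0.17/(1 − f).

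| Time | f, 12-month median | 17% reads as | f, 18-month median | 17% reads as |
|---|---|---|---|---|
| Week 9 | 11.3% | 19.2% | 7.7% | 18.4% |
| Week 12 | 14.7% | 19.9% | 10.1% | 18.9% |
| Week 15 | 18.1% | 20.7% | 12.4% | 19.4% |

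By week 15 this implies 15/(1 − 0.1807) = 18.3 or 15/(1 − 0.1244) = 17.1 registrations per 15 evaluable patients.

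**5. In counts.** Suppose three non-responders are replaced. The planned rate is 3/15 = 20.0% (95% CI 4.3% to 48.1%). With the three kept in, it is 3/18 = 16.7% (3.6% to 41.4%).

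**6. The definition against its Note.** Take a patient with ICI cycles 1 to 3, quad-shot before cycle 4, cycle 4, and a scan one cycle early, as footnote f allows. The scan shows progression and the patient is removed before cycle 5. By the definition the patient is evaluable: irradiated after at least two ICI cycles, and re-evaluated. By the Note and Section 6.6 the patient is replaced, having had one ICI cycle after radiotherapy instead of two. The text does not settle whether this documented non-responder counts. At n = 15, one patient is 1/15 = 6.7 percentage points.

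**The case against.** The strongest case against has four parts.

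*Progression.* A reader might infer that early progression in general disappears from the ORR. The documents do not support that. The sequence ends at cycle 4 or 5 and the first scheduled scan follows cycle 5 (Section 4.2 says every 5 to 6 treatments), so progression first seen there ordinarily stays in. What can be lost is clinical progression, or progression on an unscheduled scan. The case in step 6 needs both the later quad-shot slot and the earliest edge of the scan window, and removal also needs confirmed progression plus a judgement of no further benefit. It is an edge case, but the wording conflict is real.

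*Other inconsistencies.* A reader might see a contradiction between Section 4.2, which replaces anyone who does not complete treatment and investigations, and Section 6.6. Section 6.6 does not say that nobody else is replaced, and the two can be applied together with 15 evaluable patients in Section 11.3. A reader might also infer that replaced patients vanish from PFS and OS. Section 7.1.5 starts both at registration, Section 6.5 follows patients to death for survival endpoints, and nothing in Section 11.2 removes them.

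*Size.* Twelve months is the low end of the protocol's own statement, r = 0 is the extreme case, and this is a pilot with no hypothesis test. All of that stands. The interval, however, describes sampling error and cannot reveal selection.

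*Estimand.* Objective 2.1.1 concerns immunotherapy given with quad-shot, so a set that includes patients never irradiated answers a somewhat different question. This stands, and it is why the wider rate should supplement the planned one and not replace it.

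**Conclusion.** The concern holds in limited form. Patients removed before completing the sequence are replaced whatever the reason, the ORR rests on 15 evaluable patients, and no rate keeps the early failures in. The ORR is likely to be biased upward to the extent that those left out would not have responded, and it is unbiased if nobody is left out or if they would have responded equally often.

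The amount cannot be fixed from the documents. Deaths alone, under an exponential 12-month median and no responses among those left out, move a true 17% to about 19% to 21%; an assumed 18-month median gives about 18% to 19%. A lower early hazard would give less; toxicity stops and early clinical progression would add to it. The shift is small beside an interval up to 0.52 wide. It should still be fixed, because Section 11.3 sets this rate against earlier results and the remedy is a matter of wording. The conflict between the Section 7.1.1 definition and its Note does not depend on any of these assumptions.

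**What to change.** - **Section 11.1:** keep the 15-evaluable ORR and its interval. Add a prespecified ORR with a Clopper-Pearson interval over all registered patients who received at least one pembrolizumab dose. Count patients with no post-baseline assessment as non-responders, and count replaced patients who were assessed by their assessed response. Label this rate as conservative. The set with at least one radiotherapy fraction and one ICI cycle, already defined in Section 7.1.1 for toxicity, could be shown as well, but it omits losses before radiotherapy.
- **Section 11.3:** consider both rates when judging whether further studies are warranted.
- **Reporting:** give the number of replacements with reasons, and the proportion completing the sequence. The latter also bears on feasibility (objective 2.2.6).
- **Section 7.1.1:** reconcile the definition with its Note so that a patient with a documented assessment is not lost from the ORR.
- **Tidying only:** align the replacement wording of Sections 4.2 and 6.6, and the fifteen enrolled in Section 4.2 with the 15 evaluable in Section 11.3.

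The cost is wording, with no new visits or patients. The second rate will usually be somewhat lower, includes patients never irradiated, and counts losses unrelated to response as non-response. Its denominator is not fixed in advance, so the 0.52 width applies only to the evaluable rate. Patients who withdraw consent contribute data only up to withdrawal.

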### **Withdrawal of Consent**

Patients are free to withdraw from the study at any time without prejudice to further treatment.

Patients who withdraw consent for further participation in the study will not receive any further study drug or radiotherapy or further study observation. Patient will be asked for permission to use collected specimens if deemed useful by the investigator.

A patient who withdraws consent will always be asked about the reason(s) for withdrawal and the presence of any AE. The Investigator will follow up AEs outside of the clinical study.

## **7.0 Measurement of Effect**

### **7.1 Antitumor Effect – Solid Tumors**

In accordance with the standard of care, after a baseline scans obtained prior to study registration, patients will be reevaluated for response after 5 cycles of immunotherapy. Patients who continue to receive ICI at the discretion of the medical oncologist will be evaluated again after 10 cycles of ICI.

Response and progression will be evaluated in this study using the Response Evaluation Criteria in Solid Tumors (RECIST) criteria 1.1.(40) Changes in the largest diameter

(unidimensional measurement) of the tumor lesions and the shortest diameter in the case of malignant lymph nodes are used in the RECIST criteria.

### 7.1.1 Definitions

- **Evaluable for toxicity:**

Only those patients who have received at least 1 fraction of radiotherapy and at least 1 cycle of ICI will be evaluable for toxicity from the time of their first fraction of radiotherapy.

- **Evaluable for objective response:**

Only those patients who received at least one cycle of quad-shot radiotherapy (given after at least 2 cycles of ICI), and have had their target disease re-evaluated will be evaluable. These patients will have their response classified according to the definitions stated below.

Note: Per Section 6.6, subjects who are removed from study prior to completing at least 2 cycles of ICI followed by at least 1 cycle of quad-shot radiotherapy followed by at least 2 cycles of ICI will be discontinued from the study and replaced.

- **Evaluable Non-Target Disease Response.**

Patients who have lesions present at baseline that are evaluable but do not meet the definitions of target disease, have received at least one cycle of quad-shot radiotherapy, and have had their disease re-evaluated will be considered evaluable for non-target disease. The response assessment is based on the presence, absence, or unequivocal progression of the lesions.

- **Measurable disease / measurable lesions**

Measurable lesions are defined as those that can be accurately measured in at least one dimension (longest diameter to be recorded) as  $\geq 20$  mm by chest x-ray, as  $\geq 10$  mm with CT scan, or  $\geq 10$  mm with calipers by clinical exam. All tumor measurements must be recorded in millimeters (or decimal fractions of centimeters).

- **Malignant lymph nodes.**

To be considered pathologically enlarged and measurable, a lymph node must be  $\geq 15$  mm in short axis when assessed by CT scan (CT scan slice thickness recommended to be no greater than 5 mm). At baseline and in follow-up, only the short axis will be measured and followed.

- **Non-measurable disease / non-measurable lesions:**

All other lesions (or sites of disease), including small lesions (longest diameter  $<10$  mm or pathological lymph nodes with  $\geq 10$  to  $<15$  mm short axis), are considered non-measurable disease. Bone lesions, leptomeningeal disease, ascites, pleural/pericardial effusions, lymphangitis cutis/pneumonitis, inflammatory breast disease, and abdominal masses (not followed by CT or MRI), are considered as non-measurable.

### 7.1.2 Methods for Evaluation of Measurable Disease

- **Method(s) for obtaining measurements:**

All measurements should be taken and recorded in metric notation using a ruler or calipers. All baseline evaluations should be performed as closely as possible to the beginning of treatment and not more than 30 days before registration.

The same method of assessment and the same technique should be used to characterize each identified and reported lesion at baseline and during follow-up. Imaging-based evaluation is preferred to evaluation by clinical examination unless the lesion(s) being followed cannot be imaged but are assessable by clinical exam.

Clinical lesions: Clinical lesions will only be considered measurable when they are superficial (e.g., skin nodules and palpable lymph nodes) and  $\geq 10$  mm diameter as assessed using calipers (e.g., skin nodules). In the case of skin lesions, documentation by color photography, including a ruler to estimate the size of the lesion, is recommended.

- **Use of imaging techniques (e.g., x-ray, CT, MRI, PET) for measuring disease**

Imaging (CT, MRI, or PET/CT) will be obtained routinely as per clinical practice for patients being treated with immunotherapy. Either modality will be suitable for obtaining

measurements. When possible, efforts should be made to obtain the same imaging modality used for baseline imaging for all follow-up response assessments.

### 7.1.3 Response Criteria

- **Definition of complete response (CR)** for target and non-target lesions, as appropriate
  - Target Lesions:
    - Disappearance (or decrease to the point at which measurement is not possible) of all target lesions. **Any pathological lymph nodes (whether target or non-target) must have reduction in short axis to <10 mm** (the sum may not be “0” if there are target nodes)
  - Non-target lesions:
    - Disappearance (or decrease to the point at which measurement is not possible) of all non-target lesions. **All lymph nodes must be non-pathological in size (< 10 mm short axis)**
- **Definition of partial response (PR)** for target and non-target lesions, as appropriate
  - Target lesions:
    - At least a 30% decrease in the sum of diameters of target lesions, taking as reference the baseline sum of diameters
  - Non-target lesions
    - **Non-CR/Non-PD:** Persistence of 1 or more **non-target lesion(s)**.
- **Definition of progressive disease (PD)** for target and non-target lesions, as appropriate
  - Target Lesions:
    - > 20% increase in the sum of the longest diameters (SLD) taking as reference the smallest SLD recorded since the treatment started (nadir) **and minimum 5 mm increase over the nadir**
    - When sum becomes very small, increases within measurement error (2-3 mm) can lead to 20% increase
    - (Note: the appearance of one or more new lesions is also considered progressions)
  - Non-target lesions:
    - *Unequivocal progression* of existing non-target lesions. The appearance of one or more new lesions.
    - *Unequivocal progression* should not normally trump target lesion status. It must be representative of overall disease status change, not a single lesion increase
    - Although a clear progression of “non-target” lesions only is exceptional, the opinion of the treating physician should prevail in such circumstances, and the progression status should be confirmed at a later time by the review panel (or Principal Investigator).

- **Definition of stable disease (SD)** for target and non-target lesions, as appropriate
  - Target lesions:
    - Neither sufficient shrinkage to qualify for PR nor sufficient increase to qualify for PD, taking as reference the smallest sum diameters while on study
- **Definition and evaluation of best overall response**, if applicable  
The best overall response is the best response recorded from the start of the treatment across all time points.

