## 2.0 Objectives

This pilot study aims to assess the efficacy and tolerability of short-course quad-shot radiotherapy in combination with immunotherapy. Both of these standard-of-care treatments have the potential to act synergistically to improve response rates to systemic therapy. This study will study the effects of combining these standard treatments in a novel sequence. For the purposes of this study, the term immunotherapy will be used to specifically reference the use of the immune checkpoint inhibitor pembrolizumab.

The hypothesis is that the delivery of palliative quad-shot radiotherapy in combination with immunotherapy is feasible and improves the response rates at the treated site.

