#### **5.2 Secondary Outcomes**

- 5.2.1 The response rate in the target lesion measured according to RECIST 1.1 (Section 7.1.3).
- 5.2.2 The response rate in the non-target lesions (if applicable) will be measured according to RECIST 1.1 (Section 7.1.3).
- 5.2.3 The duration of response at the target lesion will be defined as the duration from the time measurement criteria are met for CR or PR (whichever is first recorded) until the first date of recurrent or progressive disease as defined in Section 7.1.4.

Quad-Shot Radiotherapy in Combination with Immune Checkpoint Inhibition for  
Advanced/Recurrent Head and Neck Cancer  
Wake Forest Baptist Comprehensive Cancer Center  
WFBCCC60320

- 5.2.4 Progression-free survival (PFS) will be defined as in Section 7.1.5.
- 5.2.5 Overall survival (OS) will be defined as in Section 7.1.5.
- 5.2.6 Tolerability will be measured using the Patient-Reported Outcomes version of the Common Terminology Criteria for Adverse Events (PRO-CTCAE).

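### Section 7.1.3 lists a new lesion at any site as target-lesion progression, so a patient can meet both target PR and target PD at one scan, and no rule says which counts in 5.2.1

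*Combined protocol and SAP*

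**What the plan says.** The hypothesis in Section 2.0 is that the combination is feasible and "improves the response rates at the treated site". Outcome 5.2.1 is the endpoint that measures this: "The response rate in the target lesion measured according to RECIST 1.1 (Section 7.1.3"). Outcome 5.2.2 refers to 7.1.3 in the same way for non-target lesions. Section 7.1.1 defines target lesions as those chosen for quad-shot radiotherapy, at most two, measured at baseline.

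Section 7.1.3 defines partial response of the target lesions by size alone: "At least a 30% decrease in the sum of diameters of target lesions". Its definition of target progression combines growth from nadir with the note "Note: the appearance of one or more new lesions is also considered progressions". The non-target definition of progression likewise lists "the appearance of one or more new lesions". Neither entry says where the new lesion must be.

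Section 11.2 counts PR or CR for each response rate, with an exact 95% interval, and adds no rule for new lesions by site.

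**The concern.** A site-level response rate should depend on the lesions at that site. Here a new lesion elsewhere, for example in the lung, is listed as progression of the irradiated lesions even when they have shrunk enough for PR. The two definitions then apply to the same lesions at the same scan, and the text does not say which prevails.

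At stake is local response with new distant disease, which is the main pattern that would separate 5.2.1 from the overall response rate. If these patients are scored as target progression, the endpoint tied to the stated hypothesis loses them. The choice would fall to the investigators who assess response, since independent review is only optional (Section 7.1.6).

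**Working it through.** **1. The plan's own figure.** Section 11.3 gives a maximum 95% Clopper-Pearson width of 0.52 with 15 patients. The lower limit is the 0.025 quantile of Beta(x, n − x + 1), and the upper limit is the 0.975 quantile of Beta(x + 1, n − x). At x = 7, n = 15 the limits are 0.213 and 0.734, a width of 0.5215. The figure reproduces.

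**2. The passages side by side**, for a patient with at least 30% shrinkage of the target lesions and a new distant lesion on the same scan:

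| Place | What it implies for this patient |
|---|---|
| 7.1.3, target PR | Target PR; no condition about new lesions |
| 7.1.3, target PD note | Target PD |
| Best-overall-response table | New lesions have their own column; any target status with a new lesion gives overall PD |
| 4.2 Study Design | Greatest response assessed separately in targeted and non-targeted lesions |
| 11.2 | Counts PR or CR; silent on precedence |

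If a new lesion always made target status PD, the table's row for any target status plus a new lesion would be redundant, because the row for target PD already covers it. The condition of no new lesions in the CR, PR and SD rows would be redundant too. The table therefore presupposes that target response and a new lesion can coexist. For 5.2.2, Section 7.1.1 bases non-target response on the lesions present at baseline and does not mention new ones.

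**3. Consequence if PD is applied.** In the table, a patient with target CR or PR and no new lesion fails overall only through non-target PD. New lesions would already have been removed from target response, which leaves unequivocal growth of an existing non-target lesion. Section 7.1.3 calls progression of non-target lesions alone exceptional. Outcome 5.2.1 would then come close to duplicating the primary ORR.

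**4. Size.** Each rescored patient moves the rate by 1/15 = 6.7 points, always downward. Let p be the treated-site response rate and q the share of target responders with a new lesion at or before their first responding scan. The recorded rate is p × (1 − q).

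- p: two quad-shot studies of radiotherapy alone in Table 2 give 6% + 47% = 53% and 28% + 49% = 77%.
- q: not in the documents; assumed 0% to 40%.

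| q | 0% | 10% | 20% | 30% | 40% |
|---|---|---|---|---|---|
| p = 53% | 53% | 48% | 42% | 37% | 32% |
| p = 77% | 77% | 69% | 62% | 54% | 46% |

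In patients, 8/15 (53%, 95% CI 27 to 79%) becomes 6/15 (40%, 95% CI 16 to 68%) if two responders are rescored, a fall of 2 × 6.7 = 13.3 points.

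**5. Timing.** The first reassessment is after 5 cycles (Section 7.1), which is 5 × 3 = 15 weeks. A new lesion at that scan leaves no earlier response to keep. If best response is taken by site, as Section 4.2 suggests, a new lesion that appears after a recorded target response does not lower the rate.

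**The case against.** The strongest reply is that the protocol, read as a whole, already gives the right answer. Target PR depends only on target diameters, the overall-response table lets target response coexist with a new lesion, and Section 4.2 takes the greatest response by site. On that reading the patient is target PR and overall PD, and nothing is lost. This stands as far as it goes: it is the better reading, and it makes any understatement conditional. It does not remove the note, which is an explicit rule under the target heading in the one section that 5.2.1 cites.

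A reader might go further and infer that 7.1.3 turns both site-specific rates into whole-patient outcomes and that treated-site response is understated. The documents do not support this.

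- Growth of existing non-target lesions never changes target status.
- The other cross-site link, the nodal clause under target CR ("Any pathological lymph nodes (whether target or non-target) must have reduction in short axis to <10 mm"), can separate CR from PR. It does not remove a patient from PR or CR, because target lesions that have disappeared also meet the 30% criterion.
- For 5.2.2 the baseline-lesion basis in Section 7.1.1 pulls the other way, and no size can be put on any effect there.

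It is also fair to say that q could be zero. Section 6.6 replaces patients removed before completing two ICI cycles, quad-shot and two further ICI cycles, so some early distant failures may leave the evaluable set. The intervals in the illustration overlap heavily, and no hypothesis test is planned.

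**Conclusion.** The point holds as an unresolved conflict within an endpoint definition. Section 7.1.3 allows target PR and target PD at the same scan, gives no precedence, and disagrees with the overall-response table and Section 4.2. For 5.2.2 it also disagrees with Section 7.1.1.

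If PD is applied, the treated-site rate can only fall, by 6.7 points per affected patient. With p of 53% the loss runs from 0 (q = 0) to about 21 points (q = 40%). With p of 77% it runs from 0 to about 31 points. These ranges rest on an assumed q, so they illustrate the effect and do not estimate it. The effect arises when the new lesion is present at or before the first responding scan. The primary ORR is not affected, because the table already makes any new lesion overall PD.

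The point is worth correcting because 5.2.1 is the endpoint that speaks to the stated hypothesis.

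**What to change.** 1. State in 7.1.3 that target response (5.2.1) and non-target response (5.2.2) are scored only on the lesions recorded in that category at baseline, as the best response across time points.
2. Move the new-lesion rule out of both site-level definitions of progression and keep it in the overall-response table.
3. Add that progression for overall response and for PFS means overall PD, including new lesions. Section 7.1.5 uses progression without defining it, so removing the two entries without this sentence would weaken the basis for counting new lesions in PFS.
4. State whether the same site-only rule ends duration of response at the target lesion. Outcome 5.2.3 refers to 7.1.4, which ends duration at progressive disease without saying whether a distant new lesion counts, so step 2 would otherwise change that endpoint silently.

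The cost is a few lines of wording. No new data are needed: target lesions are measured under 7.1.1, and Section 13.2 already lists tumor measurement and response evaluation forms. The primary ORR does not change and, with step 3 in place, neither does PFS.
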